## 6.5 RISKS MANAGEMENT PROCEDURES

### 6.5.1 Protection Against Risks

#### General Risks of Study Protocol and Procedures

- All research interventions/activities will be conducted in private patient care areas. The collection of sensitive information about subjects is limited to the amount necessary to achieve the aims of the research, so that no unneeded sensitive information is being collected.
- All demographic and clinical information about the subject will be stored on a Case Report Form which will be completed for each subject enrolled into the clinical study. A relational database will be constructed on a local server with daily backups where only select research team members will have access to the database. The electronic data capture system being used for this clinical research study has not been fully certified as being compliant with the FDA regulations at 21 CFR Part 11 due to the limited scope of this clinical research study. Data will be entered on the server over an encrypted network connection and stored behind a secure firewall. The case report forms with study IDs will be housed in the same chart as personal identifier documents are while the subject is active in the protocol. Personal information documents will be stored separately once each subject's participation is complete. Only limited team members will have access to charts and database. Other data quality assurance measures will include verifying the data, out of range data checks, and repeated evaluation of the data process. All members of the research team should receive appropriate training about securing and safeguarding research data.
- Specimens will be stripped of subject identifiers and stored according to a similar coding protocol as described above. These specimens will be stored safely in the custody of the Investigator responsible for the individual assays. The Investigators will limit future access to any remaining sample to only those investigators with prior IRB approval for their studies.
- All staff involved in this study are properly credentialed and instructed in the areas of testing, confidentiality, and safety.
- The Investigator will retain the data for the entire period of this study and will retain the specified records and reports until two years after investigations under the IND have been discontinued and the FDA is notified. The Investigator may continue to use and disclose subjects' de-identified information for the purpose of this study for a minimum of seven years after final reporting or publication of the study. If the subject decides to withdraw or be withdrawn from study participation, they may request that the study data and samples be destroyed. Subject names or other directly identifiable information will not appear on any reports, publications, or other disclosures of clinical study outcomes.

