## **2.4 STUDY ENDPOINTS**

Primary Endpoint:

The primary endpoint measures the incidences of treatment-emergent adverse events.

Secondary Endpoints:

The primary efficacy endpoint measures the change from baseline in Pulmonary Vascular Resistance (PVR) assessed by Right Heart Catheterization at 12 weeks.

Other secondary endpoints measure:

- Change from baseline in hemodynamic parameters including Cardiac Output (CO), Cardiac index (CI), mean Pulmonary Artery Pressure (mPAP), Pulmonary Artery Wedge Pressure (PAWP), Mean Right Atrial Pressure (mRAP), and compliance (SV/ (sPAP-dPAP) at 12 weeks
- Change from baseline in RV function including tricuspid annular plane systolic excursion (TAPSE) and tissue Doppler of the lateral tricuspid valve anulus (S') as assessed by echocardiograms at 12 weeks
- Change from baseline in functional exercise capacity by assessing 6 minute walk distance test with Modified Borg Dyspnea Scale at 12 weeks
- Change from baseline in the levels of serum NT-proBNP at 12 weeks
- Change from baseline in WHO Functional Class at 12 weeks
- Change from baseline in patient reported outcomes measured by PAH-SYMPACT® questionnaire at 12 weeks
- Change from baseline in daily physical activity assessed by personalized activity monitor at 12 weeks
- Pharmacokinetic endpoint: CXA-10 parent and metabolites

Exploratory Endpoints:

- Change in insulin sensitivity by intravenous glucose tolerance test at 12 weeks
- Pharmacodynamic endpoint: change from baseline in serum biomarkers, leptin, inflammatory cytokines (IL-17, IL-6, TNF $\alpha$ , MCP-1) and hsCRP at 12 weeks
- Pharmacokinetic - Pharmacodynamic relationship of CXA-10 on relevant efficacy, safety and biomarkers endpoints, if the data allow
- Epidemiological relationships of oral and gut microbiome and PAH

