## 2.5 STATISTICAL ANALYSIS

### 2.5.1 Sample Size Determination

We plan to enroll 30 subjects with PAH, allowing for a conservative drop-out rate of 10%, in this open label trial of oral CXA-10. We expect to see decrease in the PVR after 12 weeks of therapy. The intention to treat (ITT) population will consist of all subjects who have received at least one dose of study medication. To estimate our effect size for power calculations, we use data from the SUPER-1 sildenafil PAH trial (a randomized placebo control trial evaluating the effects of 20 mg, 40 mg or 80 mg TID of sildenafil in subjects with PH). Using the hemodynamic data from the 80 mg arm of the SUPER-1 trial and making a conservative assumption that our therapy will only have an effect that is 70% of sildenafil (decrease in PVR of 2.3 woods units with SD of 4.1), the sample size required for 80% power and P = 0.05 is 27 subjects (Table 2). We anticipate more than sufficient power to detect vasodilatory effects of NO2-OA administration (decreased PVR) after 3 months of therapy. Based on our extensive phase 1 data with CXA-10 formulations, we

anticipate the drug will cause no systemic blood pressure changes and no increases in methemoglobin levels.

**Table 2 Required sample size for different effect,  
Power =0.8 ,  $\alpha=0.05$ , two sided test**

% of Sildenafil	Mean (SD) PVR change, Woods unit	N
90	3.0 (4.9)	23
80	2.6 (4.2)	23
70	2.3 (4.1)	27

With safety as the primary outcome measure, we use Fleming's single stage phase II design with the following assumptions:  $\alpha = 0.05$ , Power= 0.80, lower proportion for rejection 70% (with no SAEs), higher proportion of acceptance 90% (with no SAEs) with maximum recruited patients of 27 patients resulting in a minimum number of success (with no SAEs to indicate that the treatment is safe) is 24. Thirty patients will be enrolled to compensate for up to 10% lost-to follow-up.

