#### **6.4.8. Withdrawal of Subjects and Stopping Criteria:**

##### **STOPPING RULES:**

**Dose Reduction:** If subjects experience an increase of  $\geq 7$  stools/day over baseline or any serious AE believed to be possibly related to the study drug the dose of the study drug may be reduced to 150 mg/day or 75 mg/day at the discretion of the physician investigator. Subjects may be asked to return to the clinic for an unscheduled visit to assess their status if deemed necessary

based on the clinical judgement of the physician investigator. This unscheduled visit may require blood draws, vital signs and/or review of concomitant medication.

**Withdrawal of Subjects:** Subjects must be withdrawn from the study for the following reasons:

- Systolic BP < 80 mmHg
- Liver function test abnormalities: if ALT and/or AST > 8X ULN, the subject should stop taking study drug immediately. Medical evaluation should be undertaken as appropriate to the signs and symptoms manifested by the subject
- Positive pregnancy test

Subjects may be withdrawn from the study for the following reasons:

- At their own request
- At the specific request of the Investigator (eg: detection of a new significant safety concern related to the study drug)
- Occurrence of intercurrent diseases which in investigator's opinion, continuation of the study drug would be harmful to the subject's well-being
- Pertinent non-compliance with the conditions for the trial or instructions by the investigator
- Lost to follow up

Any subject removed from the study will remain under medical supervision until the condition is medically acceptable. Study subjects removed from the study will be replaced by enrolling another volunteer with similar demographics.

Subjects not completing the entire study should be fully evaluated when possible according to the following schedule:

- If study medication is discontinued on or prior to Week 4, complete all protocol required assessments scheduled for the End of Treatment visit excluding the RHC.
- If study medication is discontinued after Week 4 but prior to Week 10, complete all protocol required assessments scheduled for the End of Treatment visit excluding the RHC.
- If study medication is discontinued on or after Week 10 and prior to the start of the End of Treatment visit, complete all protocol required assessments scheduled for the End of Treatment Period.

All withdrawn subjects will be asked to report to the clinic for a follow-up visit (Visit 9).

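### The withdrawal clause in 6.5.1 allows requests to destroy study data already collected, which conflicts with the data-retention commitment, the all-dosed population and the planned drop-out comparison, and could bias the primary adverse-event result

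*Combined protocol and SAP*

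**What the plan says.** Under the general risk protections in 6.5.1: "If the subject decides to withdraw or be withdrawn from study participation, they may request that the study data and samples be destroyed". The clause covers subjects who leave by choice and subjects whom the investigator removes. It names data and samples together and sets no limit for data already collected, adverse events or regulatory records.

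Four other parts of the document bear on it.

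- **Retention, same paragraph of 6.5.1.** "The Investigator will retain the data for the entire period of this study". The investigator also "will retain the specified records and reports until two years after investigations under the IND have been discontinued" and the FDA has been notified. The term for the records concerned is not defined.
- **Analysis population, 2.5.1.** "The intention to treat (ITT) population will consist of all subjects who have received at least one dose of study medication". No separate safety population is defined.
- **Endpoint, 2.4.** "The primary endpoint measures the incidences of treatment-emergent adverse events".
- **Withdrawal, 6.4.8.** Low systolic pressure, marked transaminase elevation and a positive pregnancy test require withdrawal. A new safety concern, the subject's own wish, intercurrent disease, non-compliance and loss to follow-up permit it. Withdrawn subjects are asked for end-of-treatment assessments and Visit 9. Then: "Study subjects removed from the study will be replaced by enrolling another volunteer with similar demographics".

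Section 2.5.5 also plans to compare the baseline characteristics of subjects who do and do not finish, and to weigh reasons for missing data and any early post-baseline values.

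**The concern.** A rule that stops further collection when consent is withdrawn is ordinary. A rule that lets data already collected be destroyed is different, because the analysis plan depends on those data. A dosed subject whose data have been erased cannot be in an all-dosed population, cannot be compared with completers, and contributes no adverse events, exposure or laboratory values.

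The primary endpoint is safety, and some withdrawals are caused by safety findings. Erasure could therefore be related to the outcome. If it is, events leave both numerator and denominator, and replacement may fill the place with a subject who has no event. The trial is small enough for a few such subjects to matter, and erased data cannot be recovered at analysis.

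**Working it through.** **1. Can the commitments be met together?**

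| Commitment | Section | If a request is granted |
|---|---|---|
| Keep the data throughout the study | 6.5.1 | Broken for that subject |
| Keep specified records beyond the end of IND work | 6.5.1 | Unclear, because the records are not defined |
| Analyse everyone dosed at least once | 2.5.1 | Cannot be done for that subject |
| Compare completers with non-completers | 2.5.5 | Cannot be done for that subject |

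No section says how a request is reconciled with these.

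**2. Direction of the effect on incidence.** With x subjects having an event among n dosed, x < n:

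- erasing a subject with an event changes the incidence by (x − 1)/(n − 1) − x/n = (x − n)/[n(n − 1)], which is negative;
- erasing a subject without one gives x/(n − 1), which is not below x/n.

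The result moves towards safe only if subjects with events are erased more often than subjects without.

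**3. The plan's safety rule.** Section 2.5.1 gives N = 27, at least 24 SAE-free, alpha 0.05, power 0.80, with reference rates of 70% and 90%. With X binomial(27, p), the exact values are:

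- P(X ≥ 24 | p = 0.70) = 0.020, within the stated alpha;
- P(X ≥ 24 | p = 0.90) = 0.718, below the stated power.

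The power shortfall is a separate matter, and nothing here rests on it. The baseline for the next step is 0.020.

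**4. Illustration with the same rule.** Assume a true SAE-free rate of 70%. Assume that a share r of subjects with an SAE withdraw, ask for erasure, have it granted and are replaced, so that 27 remain. The documents give no value for r.

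- SAE-free rate among those retained: p′ = 0.7 / [0.7 + 0.3(1 − r)]
- Chance of passing: P(X ≥ 24 | 27, p′)
- Expected number erased while filling 27 places: 27/(1 − 0.3r) − 27

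| r | p′ | Chance of passing 24/27 | Expected erased |
|---|---|---|---|
| 0 | 0.700 | 0.020 | 0 |
| 10% | 0.722 | 0.035 | 0.8 |
| 20% | 0.745 | 0.059 | 1.7 |
| 30% | 0.769 | 0.100 | 2.7 |
| 50% | 0.824 | 0.273 | 4.8 |

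The chance reaches 0.05 at r of about 17%. The last row is shown to mark the limit of plausibility: it needs about 4.8 erased and replaced subjects, but planned enrolment of about 30 leaves only 30 − 27 = 3 spare places, which are also meant to cover ordinary drop-out.

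**The case against.** The case on the other side is substantial, and most of it narrows the point.

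- **A request is not an erasure.** The clause lets subjects ask; it does not say that requests are granted. The same paragraph commits to keeping the data and foresees use of de-identified information for at least seven years. A reader might infer that withdrawn subjects' data will be destroyed, but the documents do not say so. They also give no ground for refusing, so the conflict stands unresolved.
- **SAEs would not disappear.** A reader might infer that serious events could vanish altogether. Section 6.4.2 sends adverse events to the investigators and the IRB, and SAE outcomes to the IRB, the drug supplier and the IND sponsor. Section 6.4.6 adds FDA and NHLBI reporting for defined categories of event. The monitoring board reviews cumulative data, and 6.4.3 includes withdrawals in what is monitored. Reports already sent would survive. They would not restore exposure, laboratory values, a full record of non-serious events or the subject's place in the denominator.
- **The clause is not confined to safety withdrawals.** It covers all of them, and erasure unrelated to events has no systematic direction (step 2). The named mandatory triggers are not in themselves SAEs under 6.4.5. For a possibly related SAE, 6.4.8 provides for discretionary dose reduction and does not list an SAE as a mandatory reason for withdrawal. The link from safety withdrawal to the 24-of-27 rule is therefore possible but not shown.
- **IND record retention.** A reader might infer a breach. It cannot be shown, because the specified records are undefined.
- **Replacement.** Section 6.4.8 does not say that a replaced subject leaves the analysis, and 2.5.1 keeps everyone dosed.
- **Efficacy.** Subjects who stop before Week 10 have no end-of-treatment catheterization in any case, so for them erasure removes no paired PVR change.

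The consent text was not available for this review and may limit the request.

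**Conclusion.** The concern holds as a conflict within the document. Section 6.5.1 permits requests to destroy collected data without exception. Granting one is incompatible with the retention commitment in the same paragraph, with the all-dosed population and with the planned drop-out comparison.

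Its effect on the primary endpoint is possible, not demonstrated. It depends on requests being made, being granted, and coming more often from subjects with events. The most exposed information is non-serious treatment-emergent events, laboratory values and the denominator.

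The 24-of-27 figures (0.020 rising to 0.035, 0.059 and 0.100 for r of 10%, 20% and 30%) show sensitivity under an assumed r and a true SAE-free rate of 70%. They are not an estimate of what will happen. Below r of about 17% the chance of wrongly passing stays under 0.05, and the 0.273 at r = 50% does not fit planned enrolment.

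The severity is should-fix, not must-fix: the likely frequency is unknown and may be low, but the loss would be irreversible and the correction is simple.

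**What to change.** In 6.5.1, and in the consent text if it says the same, replace the sentence with wording to this effect:

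- after consent is withdrawn, no further study data are collected;
- all data collected up to withdrawal, including adverse events, laboratory values and dosing, are retained and analysed;
- a request for destruction applies only to stored research samples that have not been analysed.

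In 2.5.1 or 2.5.2, state that every dosed subject stays in the safety analysis whatever their withdrawal status, including those who are replaced under 6.4.8. In 6.5.1, define the specified records.

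The cost is a few sentences and IRB approval, with no added visits, subjects or procedures. The real downside is that withdrawing subjects can no longer have data already collected erased, so the consent discussion must say this plainly.

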## **6.5.2 Protection Against Potential Risks of Experimental Intervention**

Blood Draws: To minimize the risks of blood drawing, a licensed technician or registered nurse will perform the procedure and standard aseptic technique will be followed to avoid the very rare complication of infection.

Echocardiography: There are no known risks from echocardiography.

Right Heart Catheterization: The procedures will only be performed by trained and experienced clinicians. Subjects will be closely monitored as is routinely done for such procedures.

Six Minute Walk Test: Risks normally associated with 6 minute walk testing will be minimized by selecting study personnel who are experienced with these testing procedures and who have the facilities and equipment necessary to complete the testing.

IVGTT: To minimize the risk associated with the IVGTT, subjects will be closely monitored for signs and symptoms of hypoglycemia.

Confidentiality: Risk to confidentiality will be minimized by identifying data collected only by anonymous study number. A confidential database linking subject identifying information with study ID number will be maintained in a password-protected computer, and access to the database will be limited to the research staff under the supervision of the PI. All data storage and transfer including imaging and physiology data will be secure and HIPAA compliant. At no time will human subjects be identified in data presentation, publications etc. Specimens will be stripped of subject identifiers and stored according to a similar coding protocol as described above. These specimens will be stored securely in the custody of the investigators responsible for the individual assays. All staff involved in this study are properly credentialed and instructed in the areas of testing, confidentiality, and safety.

Certificate of Confidentiality: To further protect the privacy of study participants, a Certificate of Confidentiality will be issued by the National Institutes of Health. This certificate protects identifiable research information from forced disclosure. It allows the investigator and others who have access to research records to refuse to disclose identifying information on research participation in any civil, criminal, administrative, legislative, or other proceeding, whether at the federal, state, or local level. By protecting researchers and institutions from being compelled to disclose information that would identify research participants, Certificates of Confidentiality help achieve the research objectives and promote participation in studies by helping assure confidentiality and privacy to participants.

Protection of Human Subjects Education: The PI, sub-investigators and all involved research staff are trained in human research protection issues and have completed the Collaborative Institutional Training Initiative (CITI) online courses including education in Human Subject Research and Responsible Conduct of Research. The courses consist of modules on Informed Consent, the Consent Process, Research Integrity and Conflict of Interests, Research and Health Insurance Portability and Accountability Act (HIPAA) Privacy Protections. Any new research staff will be required to complete the CITI online courses before engaging in human subjects research and being added to a research protocol. In addition, all members of the research team must continue to supplement this training by completing a refresher course every three years.

Safety Oversight: An external Data and Safety Monitoring Board will be established to monitor the study.

## 7. COSTS AND PAYMENTS

### 7.1 COSTS

Research subjects or their insurance providers will not be charged for any of the procedures performed for the purpose of this research study.

### 7.2 PAYMENTS

The subjects will receive the remuneration upon completion of the study. In the event that a subject drops out prior to completion of the study due to study related adverse events, the subject

will be reimbursed for the individual study visits that they completed. Travel expenses may also be reimbursed.

## 8.2 SOURCES OF SUPPORT

National Institutes of Health

**APPENDIX A: Schedule of Procedure.**

Study Phase	Screening	Treatment Period									End Tx	End Tx	End Tx	F/U
Study Visit	V1	V2	V3	V3a	V3b	V4	V4a	V5	V5a	V6	V7	V8	V9	
	clinic	clinic	Clinic	Clinic	phone	clinic	phone	clinic	phone	clinic	clinic	clinic	clinic	
Study Procedure	W-4 ~1	Week 0	Week 0	Week 1	Week 2	Week 4	Week 6	Week 8	Week 10	Week 12 d post Tx	Week 12 d post Tx	Week 16 d post Tx		
Informed Consent	x													
Inclusion/Exclusion Criteria	x													
Med Hx & Demographics	x													
Complete Physical Exam	x													
Brief Physical Exam		x				x		x		x	x		x	
Weight & Height #	x	x				x		x		x			x	
ECG	x	x				x		x		x				
Vital Signs□	x	x				x		x		x			x	
Clinical Lab Tests & Urinalysis	x	x				x		x		x			x	
Hemoglobin A1C test	x										\$x			
PT/INR	x	x		x◊							x			
NT Pro-BNP	x	x				x		x		x			x	
Pregnancy test *	x	x				x		x		x			x	
Pulmonary Function Test §	x													
Echocardiogram		x¹									x			
RHC	x^										x			
Acute pharmacological responses evaluation ¥	x										x			
6MW with Borg Dyspnea Scale	x		x			x		x			x		x	
PAH-SYMPACT®		x				x		x		x				
WHO Functional Class Assessment	x	x				x		x		x			x	
Dispense Study Drugs			x			x		x						
Population PK blood sampling	x		x			x		x			x	x		
Research blood samples for biomarkers, cytokines measurements	x	x	x			x		x		x	x	x	x	

Research oral and stool samples for microbiome analysis	x									x		
Intravenous glucose tolerance test		x								x		
Provide accelerometer	x							x				
Return accelerometer data		x								x		
Concomitant Medications Assessment	x	x	x		x	x	x	x	x	x	x	x
AE Assessment	x	x	x		x	x	x	x	x	x	x	x

